## **10.1.10. Publication Policy**

- Where possible, primary manuscripts reporting results of the primary efficacy endpoint or the final results will be submitted for publication within 12 to 18 months of the primary evaluation date or end of study, whichever is earlier.
- Investigators who participate as authors in manuscripts derived from Alexion-sponsored studies will agree to the prerequisites as outlined in the Alexion author engagement agreement prior to engaging in manuscript development.
- The Investigator agrees to submit proposals for new manuscripts (whether or not the proposed analyses are derived from protocol-specified endpoints) to Alexion for review and consideration. All manuscripts or abstracts emanating from approved proposals are to be submitted to Alexion for review before submission to the journal/society. This allows Alexion to protect proprietary information and provide comments.
  - The proprietary nature of some development work may preclude publication. In some cases, it may be necessary to delay a publication to allow Alexion to ensure protection of intellectual property.
- Primary publications, including congress and journal publications, containing the protocol-specified results of a study should occur prior to the publication of individual study site results or case reports. Alexion's policy prohibits duplicate publication, whereby the same results must not be published in multiple peer-reviewed journal manuscripts.
  - Encore congress publications may be appropriate to allow communication of research findings to relevant audience and geographical regions.
- Alexion will comply with the requirements for publication of study results as defined by the Pharmaceutical Research and Manufacturers of America and the International Committee of Medical Journal Editors and per the Alexion Publication Policy. In accordance with standard editorial and ethical practice, Alexion will generally support publication of multicenter studies only in their entirety and not as individual site data. In this case, a Coordinating Investigator will be designated by mutual agreement.
- Authorship will be determined by mutual agreement and in line with International Committee of Medical Journal Editors authorship requirements and per the Alexion Publication Policy.
- Alexion will publish Patient Lay Summaries and include participants and/or caregivers as reviewers for readability and understanding of lay person language.

## 10.1.11. Good Clinical Practice Compliance

Alexion and any third party to whom aspects of the study management or monitoring have been delegated will undertake their assigned roles for this study in compliance with all applicable industry regulations, ICH GCP Guideline E6 R2, EU Directive 2001/20/EC, as well as all applicable national and local laws and regulations.

Visits to sites are conducted by representatives of Alexion and/or the company organizing/managing the research on behalf of Alexion to inspect study data, participants' medical records, and eCRFs in accordance with current GCP and respective local and (inter)national government regulations and guidelines. Records and data may additionally be reviewed by auditors or by regulatory authorities.

Alexion ensures that local regulatory authority requirements are met before the start of the study. Alexion (or designee) is responsible for the preparation, submission, and confirmation of receipt of any regulatory authority approvals required prior to release of study intervention for shipment to the site.

## **10.2.** Clinical Laboratory Tests

- The tests listed in Table 11 will be performed by the central or specialty laboratory as appropriate for all participants unless otherwise noted. However, if a participant is not able to present to the clinic, a local laboratory may be used to collect the protocol-required samples.
- Protocol-specific requirements for inclusion or exclusion of participants are detailed in Section 5.
- Additional tests may be performed at any time during the study as determined necessary by the Investigator or required by local regulations.
- Women of childbearing potential should only be enrolled after a negative serum pregnancy test result at the Screening Visit and a negative urine pregnancy test at Day 1. Additional serum or urine pregnancy testing will be employed as required by site policies, local regulations, or per the requirements of the IRB/IEC and should be performed per the time points specified in the SoA (Table 2, Table 3, and Table 4).
- Investigators must document their review of each laboratory report. Clinically significant findings resulting in an assessment of a TEAE should be recorded on the AE eCRF.
- Laboratory/analyte results that could unblind the study will not be reported to investigational sites or other blinded personnel until the study has been unblinded.

Laboratory Assessments	Parameters		
Hematology	Platelet count RBC count Hemoglobin Hematocrit	RBC indices : Distribution width Mean corpuscular volume Mean corpuscular hemoglobin % Reticulocytes	WBC count with differential: Neutrophils Lymphocytes Monocytes Eosinophils Basophils
Clinical Chemistry	BUN C-reactive protein Creatinine Chloride Potassium Bicarbonate Sodium Glucose (nonfasting) Creatine kinase	AST/SGOT ALT/SGPT Alkaline phosphatase Gamma glutamyltransferase Total and direct bilirubin Total protein Albumin Uric acid	Lipids : Total cholesterol Triglycerides LDL-c HDL-c
Coagulation	International normalized ratio, partial thromboplastin time, prothrombin time		

Table 11: Protocol-Required Laboratory Assessments

#### Table 11: Protocol-Required Laboratory Assessments

Laboratory Assessments	Parameters	
Urinalysis	Appearance, color, specific gravity, pH, glucose, protein, leukocyte esterase, blood, ketones, bilirubin, urobilinogen, nitrite, microscopic examination (if blood or protein is abnormal)	
Screening tests	Serum/urine beta-hCG pregnancy test (as needed for female participants of child-bearing potential) Serum follicle-stimulating hormone test (as needed for female participants who	
	HIV-1 and HIV-2 antibodies Hepatitis B surface antigen Hepatitis C antibody	
Complement activity	Pharmacodynamic assays (AP activity and Bb concentration) Complement biomarkers (Factor D, C3, C5b-9, Properdin, and CP activity)	
Other	Biomarker assay (anti-AChR antibody) Pharmacokinetic assay (serum ALXN2050 concentration) Nongenetic exploratory biomarkers (eg, MuSK, LRP4, MMP-10, IL-6)	

Abbreviations: AChR = acetylcholine receptor; ALT = alanine aminotransferase; AP = alternative pathway; AST = aspartate aminotransferase; Bb = Bb fragment of complement factor B; BUN = blood urea nitrogen; C = complement component; C5b-9 = terminal complement complex; CP = classical pathway; eCRF = electronic case report form; hCG = human chorionic gonadotropin; HDL-c = high-density lipoprotein cholesterol; HIV-1 = human immunodeficiency virus type 1; HIV-2 = human immunodeficiency virus type 2; IL = interleukin; LDL-c = low-density lipoprotein cholesterol; LRP4 = low density lipoprotein receptor-related protein 4; MMP-10 = matrix metalloproteinase-10; MuSK = muscle-specific tyrosine kinase; RBC = red blood cells; SGOT = serum glutamic oxaloacetic transaminase; SGPT = serum glutamic pyruvic transaminase; WBC = white blood cells

## 10.3. Adverse Events: Definitions and Procedures for Recording, Evaluating, Follow-up, and Reporting

#### 10.3.1. Definition of AE

#### **AE Definition**

- An AE is any untoward medical occurrence in a participant or clinical investigation participant administered a pharmaceutical product and which does not necessarily have to have a causal relationship with this treatment (ICH E2A).
- Note: An AE can therefore be any unfavorable and unintended sign (including an abnormal laboratory finding), symptom, or disease [new or exacerbated] temporally associated with the use of the study intervention, whether or not considered related to the study intervention.

#### Events Meeting the AE Definition

- Any abnormal laboratory test results (hematology, clinical chemistry, or urinalysis) or other safety assessments (eg, ECG, radiological scans, vital signs measurements), including those that worsen from baseline, considered clinically significant in the medical and scientific judgment of the Investigator (ie, not related to progression of underlying disease).
- Exacerbation of a chronic or intermittent pre-existing condition including either an increase in frequency and/or intensity of the condition.
- New conditions detected or diagnosed after study intervention administration even though it may have been present before the start of the study.
- Signs, symptoms, or the clinical sequelae of a suspected drug-drug interaction.
- Signs, symptoms, or the clinical sequelae of a suspected overdose of either study intervention or a concomitant medication. Overdose per se will not be reported as an AE/SAE unless it is an intentional overdose taken with possible suicidal/self-harming intent. Such overdoses should be reported regardless of sequelae.

#### **Events Not Meeting the AE Definition**

- Medical or surgical procedure (eg, endoscopy, appendectomy): The condition that leads to the procedure is the AE. Situations in which an untoward medical occurrence did not occur (eg, hospitalization for elective surgery if planned before signing the ICF, admissions for social reasons or for convenience).
- Anticipated day-to-day fluctuations of pre-existing disease(s) or condition(s) present or detected at the start of the study that do not worsen.
- A medication error (including intentional misuse, abuse, and overdose of the product) or use other than what is defined in the protocol is not considered an AE unless there is an untoward medical occurrence as a result of a medication error.
- Cases of pregnancy that occur during maternal or paternal exposure to study intervention are to be reported within 24 hours of Investigator/site awareness. Data on fetal outcome and breastfeeding will be collected for regulatory reporting and safety evaluation.

#### Events Not Meeting the AE Definition

- Any clinically significant abnormal laboratory findings or other abnormal safety assessments which are associated with the underlying disease, unless judged by the Investigator to be more severe than expected for the participant's condition.
- The disease/disorder being studied or expected progression, signs, or symptoms of the disease/disorder being studied, unless more severe than expected for the participant's condition.
- Situations in which an untoward medical occurrence did not occur (social and/or convenience admission to a hospital).
- "Lack of efficacy" or "failure of expected pharmacological action" per se will not be reported as an AE or SAE. Such instances will be captured in the efficacy assessments. However, the signs, symptoms, and/or clinical sequelae resulting from lack of efficacy will be reported as AE or SAE if they fulfill the definition of an AE or SAE.

## **10.3.2. Definition of SAE**

If an event is not an AE per definition above, then it cannot be an SAE even if serious conditions are met (eg, hospitalization for signs/symptoms of the disease under study, death due to progression of disease).

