### 8.2.5. Clinical Deterioration of Myasthenia Gravis

Clinical Deterioration of MG is defined as any of the following:

- Patients who experience an MG Crisis, which is defined as weakness from MG that is severe enough to necessitate intubation or to delay extubation following surgery. The respiratory failure is due to weakness of respiratory muscles. Severe bulbar (oropharyngeal) muscle weakness often accompanies the respiratory muscle weakness, or may be the predominant feature in some patients; or,
- A score of 3 or a 2-point worsening from baseline on any one of the individual MG-ADL items other than double vision or eyelid droop that, in the Investigator's assessment, is associated with significant symptomatic worsening; or,

• Administration of rescue therapy for MG to a patient whose, in the opinion of the Investigator or Investigator-designated clinician, health would be in jeopardy if rescue therapy were not given (eg, emergent situations).

Alexion or designee should be notified within 24 hours of initiation of treatment with rescue therapy for Clinical Deterioration of MG.

Evaluation of Clinical Deterioration of MG must be performed as soon as possible (ie, within 48 hours of notification to the Investigator of symptom onset). If a participant experiences Clinical Deterioration of MG during a scheduled study visit or presents to the clinic after an event of Clinical Deterioration of MG, refer to the SoA (Section 1.3) for assessments/procedures to be obtained. Additional tests may be performed in the best judgment of the Investigator.

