# 8.10. Health Economics Data and/or Medical Resource Utilization

Medical resource utilization and/or health economics data will not be collected during this study.

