## 9.6. Data Monitoring Committee

A Data Monitoring Committee will not be convened for Study ALXN2050-MG-201.

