5.6.1.2.5. Deaths and Other AEs

For TEAEs leading to study intervention discontinuation or death, the number of events, the number and percentage of participants with events, and the event rate of TEAEs per 100 patient-years will be presented by SOC and PT. Listings of TEAEs leading to study intervention discontinuation or death will be produced as well.

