5.7.5. Hospitalizations

Hospitalization data will be listed by treatment group using the SS at Analyses 1 and 2.

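### The AE and SAE rules conflict for worsening MG, so a hospitalization or death from MG can fall outside the TESAE and death tables on an undefined judgement

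*Protocol*

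**What the plan says.** **Definitions.** Protocol Section 10.3.1 has two lists. The events that meet the AE definition include "Exacerbation of a chronic or intermittent pre-existing condition including either an increase in frequency and/or intensity of the condition", with no exception for MG. The events that do not meet it include "The disease/disorder being studied or expected progression, signs, or symptoms of the disease/disorder being studied, unless more severe than expected" for that participant. Nothing says how expected severity is to be judged. Section 10.3.2 opens with a conditional rule: an event that is not an AE under the preceding definition "cannot be an SAE even if serious conditions are met (eg, hospitalization for signs/symptoms of the disease under study, death due to progression of disease"). The seriousness criteria that follow include death, life-threatening events and inpatient hospitalization.

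**Notice to the sponsor.** Section 8.2.5 defines Clinical Deterioration (CD) as an MG crisis, a marked worsening on a non-ocular MG-ADL item, or rescue therapy given because health would otherwise be in jeopardy. It adds that "Alexion or designee should be notified within 24 hours of initiation of treatment with rescue therapy for Clinical Deterioration of MG". Section 6.5.3 sets the same trigger.

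**Hospitalizations.** Protocol Section 8.10 states that "Medical resource utilization and/or health economics data will not be collected during this study". SAP Section 5.7.5 states that "Hospitalization data will be listed by treatment group using the SS at Analyses 1 and 2".

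**Outputs and oversight.** The AE tables in SAP Section 5.6.1.2 are built from TEAEs. For deaths, Section 5.6.1.2.5 gives tables of TEAEs leading to death and adds that "Listings of TEAEs leading to study intervention discontinuation or death will be produced as well". No listing of all deaths is specified. Protocol Section 9.6 states that "A Data Monitoring Committee will not be convened for Study ALXN2050-MG-201".

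**The concern.** The safety objective is to characterize ALXN2050 against placebo, with the incidence of TEAEs and TESAEs as an endpoint. In an MG trial, worsening MG is an event that an investigator could reasonably attribute to the disease. If the definitions let one site report an MG admission as an SAE and another leave it out, the TESAE and death counts depend partly on which list a site applies.

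Arms this small have little room for that. A table with no serious MG event could mean that none occurred, or that those that occurred were judged to be expected disease, and the reader of the report could not tell which. An event never classed as an AE also does not start the 24-hour SAE report in Section 10.3.4.

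**Working it through.** The plan states no figure on this point, so there is none to reproduce. The check sets the rules side by side, follows an event through the planned outputs, and then shows how much one event weighs.

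**1. The same event under each rule**

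| Event | 10.3.1, events that meet the definition | 10.3.1, events that do not | 10.3.2 |
|---|---|---|---|
| MG admission judged in line with the participant's condition | AE (exacerbation) | Not an AE | Not an SAE; a named example |
| MG admission judged worse than expected | AE | Exclusion does not apply | SAE (hospitalization) |
| Death attributed to expected MG progression | AE (exacerbation) | Not an AE | Not an SAE; a named example |
| MG crisis | AE (exacerbation) | Not an AE unless judged worse than expected | Not named; SAE if it is an AE |

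Rows 1 and 3 are the conflict. Rows 1 and 2 differ only by a judgement that has no stated criterion. By contrast, Section 10.7 requires any seizure or suspected seizure to be reported within 24 hours as a TESAE. MG crisis has no comparable rule.

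**2. Where an event not classed as an AE would appear**

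- *TESAE and death tables (SAP 5.6.1.2.1 to 5.6.1.2.5):* absent, because both start from TEAEs.
- *24-hour notice (Protocol 6.5.3, 8.2.5):* triggered by the start of rescue therapy. A crisis, admission or death without rescue does not trigger it.
- *CD tables (SAP 5.5.1.6, 5.5.2.5):* included if the event meets the CD definition. They count CD by group but do not show seriousness or death. They are exploratory, and Section 1.2 of the addendum cancels exploratory endpoint analyses for the final report.
- *Hospitalization listing (SAP 5.7.5):* kept, since the addendum retains planned listings other than those for exploratory biomarkers. The Schedules of Activities contain no hospitalization item and the case report form is not in the documents, so it is unknown whether the listing draws on anything beyond AE forms.
- *End of Study visit (Protocol Tables 2 to 4):* AE review is scheduled; MG-ADL and CD assessment are not.

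**3. Weight of one event**

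Inputs: 70 participants (Protocol 9.2), allocated 2:1:2 (6.3.1).

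- Arm sizes: 70 × 2/5 = 28; 70 × 1/5 = 14; 70 × 2/5 = 28.
- One omitted participant: 1/28 = 3.6%; 1/14 = 7.1%. The second figure applies to the Primary Evaluation Period (PEP) only, because re-randomization later adds about 28/2 = 14 participants on 120 mg (Group 3b).
- One-sided 95% upper limit when no event is reported, 1 − 0.05^(1/n): n = 28 gives 10.1%; n = 14 gives 19.3%. These limits hold only if every event is captured.

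**4. Illustration under assumed rates**

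The documents give neither an 8-week rate of serious MG events nor a probability that an investigator classes one as an AE. Both are assumed here.

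- Chance of at least one event among 28, 1 − (1 − r)^28: r = 1%, 2%, 5%, 10% gives 24.5%, 43.2%, 76.2%, 94.8%.
- Chance that two true events are both missing from the TESAE table, (1 − q)², with independent classification: q = 75%, 50%, 25% gives 6%, 25%, 56%.

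**The case against.** **The SAE bar is conditional.** A reader might infer from the examples in Section 10.3.2 that an MG hospitalization or MG death can never be an SAE. The text does not say so. The bar covers only events already excluded as AEs, and Section 10.3.1 keeps an MG event that is worse than expected. One can also read the exacerbation item as the general rule and the disease-under-study item as the specific one. That is a fair reading, but the protocol does not state it, and the threshold stays undefined.

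**Other text favours reporting.** Sequelae of lack of efficacy are to be reported if they meet the AE or SAE definition, and doubtful hospitalizations are to be treated as serious. The first refers back to the definition in dispute. The second applies to something already called an AE. Neither settles the matter.

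**Crisis is a weak example.** Section 10.3.2 does not name it. Participants enter at MGFA Class II to IV, and intubation is Class V, so a crisis readily qualifies as worse than expected. This stands: the clearer gap is MG hospitalization and MG death.

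**Events would not go unseen.** A reader might infer that nobody would see these events by arm. That is too strong. CD was planned by arm at Week 8 with differences and 90% confidence intervals, hospitalizations are listed by arm, and select sponsor staff are unblinded from the PEP analyses onward (Protocol 6.3.2). Immediate safety concerns go to the sponsor (Section 8), withdrawals are notified with reasons recorded (7.2), and postmortem findings are supplied after a death (10.3.3). These routes make it unlikely that a serious event passes unnoticed. They do not put it in the TESAE or death tables, and they assign no one a by-arm safety review during the PEP. The optional interim look in Section 9.5 is for Phase 3 planning only.

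**No in-study rate supports a larger claim.** It is tempting to apply the 1.5% mortality in Section 2.2.1 to 70 participants (0.015 × 70 = 1.05), but that figure has no time denominator that fits this trial. The 15% to 20% crisis figure covers the disease course. The documents do not describe rebound after stopping treatment, so no argument can rest on it.

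**Conclusion.** The point holds in a limited form. The AE and SAE definitions are inconsistent for worsening MG, and whether an MG hospitalization or MG death is counted rests on an undefined investigator judgement. Following the plan as written can leave such an event out of the TESAE outputs and the tables of TEAEs leading to death. The CD tables and hospitalization listing compensate in part. There is no Data Monitoring Committee, and no body is assigned by-arm safety review during the PEP.

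The number of events affected cannot be estimated from the documents. What can be said is that each one is 3.6% of a 28-participant arm, or 7.1% of the 14-participant arm during the PEP, assuming enrolment as planned. The rates in step 4 are assumptions.

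Two things remain unknown: what the case report form collects on hospitalization, and whether the Week 8 CD table was kept, since the separate Week 8 addendum of 20 Dec 2023 is not among the documents. The addendum's cuts followed termination for lack of efficacy and are not a fault of the original design. This is an inexpensive improvement to the completeness of the safety comparison; it is not evidence that harms were hidden.

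**What to change.** 1. **Protocol 10.3.1, 10.3.2 and 8.2.5:** reconcile these passages so that one stated rule covers MG events that meet a seriousness criterion. It should say whether the exacerbation item applies to MG, how expected severity is judged if that exception stays, and whether such an event is reported when no rescue therapy is given.
2. **SAP 5.6.1.2.5:** list all deaths by arm, whatever their AE classification.
3. **SAP 5.6 or 5.7.5:** list MG crises and MG hospitalizations by arm on the same basis, and name the data source.
4. **SAP 5.6.1.2:** show TESAEs with and without MG-related preferred terms, so that disease events do not obscure other signals.

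The cost is protocol wording, a few more reports, an extra listing and one split of an existing table. TESAE counts would rise somewhat, and item 4 makes that visible. The study has been terminated, so item 1 cannot change how past events were classified. Items 2 to 4 can still be added to the final report, as far as the data were collected, because the addendum keeps all safety analyses on data to the end of the study.
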